### 14.1 Adverse Event Collection in the Case Report Forms

All adverse events that occur beginning with start of treatment (minus exceptions defined in Section 10.0) must be captured in the Toxicity Form. Baseline AEs should be captured on the Medical History Form.

Participant death due to disease progression should be reported on the Toxicity Form as grade 5 disease progression. If death is due to an AE (e.g. cardiac disorders: cardiac arrest), report as a grade 5 event under that AE. Participant death must also be recorded on the

Death Form.

## **15 MEASUREMENT OF EFFECT**

Criteria for clinical complete response:

- No residual gross tumor at procto/sigmoidoscopy; or only erythematous scar or ulcer
- No palpable tumor on DRE
- No radiographic evidence of tumor on MRI
- No suspicious mesorectal lymph nodes on MRI
- Negative biopsy from scar, ulcer, or former tumor site (if necessary according to surgeon's judgment)

Criteria for not clinical complete response (also known as clinical partial response):

- Does not meet criteria for cCR or progressive disease
  - Residual disease by DRE, endoscopy or MR.

Criteria for progressive disease:

- Increase in size of primary tumor by RECIST criteria (increase of at least 20% from nadir in the sum of the target lesion, with an absolute increase of at least 5 mm)
- New metastatic disease

## **16 DATA AND SAFETY MONITORING PLAN**

In compliance with the Washington University Institutional Data and Safety Monitoring Plan, the Siteman Cancer Center independent standing Data and Safety Monitoring Board (DSMB) will be specifically convened for this trial to review toxicity data. This DSMB will consist of clinical investigators with expertise in multiple modalities and at least one biostatistician. Members of this DSMB are subject to the Washington University School of Medicine policies regarding standards of conduct. Individuals invited to serve on the DSMB will disclose any potential conflicts of interest to the trial principal investigator and/or appropriate university officials in accordance with institution policies. Potential conflicts that develop during a trial or a member's tenure on a DSMB must also be disclosed.

Until such a time as the first secondary site enrolls its first patient, a semi-annual DSM report to be prepared by the study team will be submitted to the Quality Assurance and Safety Monitoring Committee (QASMC) semi-annually beginning six months after study activation at Washington University (if at least one patient has been enrolled) or one year after study activation (if no patients have been enrolled at the six-month mark).

The DSM report for the DSMB will be prepared by the study team with assistance from the study statistician, will be reviewed by the DSMB, and will be submitted to the QASMC. The DSMB must meet at least every six months beginning six months after enrollment of the first patient at a secondary site, no more than one month prior to the due date of the DSM report to QASMC. This report will include:

- HRPO protocol number, protocol title, Principal Investigator name, data coordinator name, regulatory coordinator name, and statistician
- Date of initial HRPO approval, date of most recent consent HRPO approval/revision, date of HRPO expiration, date of most recent QA audit, study status, and phase of study
- History of study including summary of substantive amendments; summary of accrual suspensions including start/stop dates and reason; and summary of protocol exceptions, error, or breach of confidentiality including start/stop dates and reason
- Study-wide target accrual and study-wide actual accrual including numbers from participating sites
- Protocol activation date at each participating site
- Average rate of accrual observed in year 1, year 2, and subsequent years at each participating site
- Expected accrual end date, accrual by site
- Objectives of protocol with supporting data and list the number of participants who have met each objective
- Measures of efficacy
- Early stopping rules with supporting data and list the number of participants who have met the early stopping rules
- Summary of toxicities at all participating sites
- Abstract submissions/publications
- Summary of any recent literature that may affect the safety or ethics of the study

Further DSMB responsibilities are described in the charter.

The study principal investigator and coordinator will monitor for serious toxicities on an ongoing basis. Once the principal investigator or coordinator becomes aware of an adverse event, the AE will be reported to the HRPO and QASMC according to institutional guidelines (please refer to Section 10.0).

Refer to the Washington University Quality Assurance and Data Safety Monitoring Committee Policies and Procedures for full details on the responsibilities of the DSMB. This is located on the QASMC website at <https://siteman.wustl.edu/research/clinical-research-resources/protocol-office-prmcqasmc/>

## 17 AUDITING

As coordinating center of this trial, Washington University (via the Quality Assurance and Safety Monitoring Committee (QASMC) will monitor each participating site to ensure that all protocol requirements are being met; that applicable federal regulations are being followed; and that best practices for patient safety and data collection are being followed per protocol. Participating sites will be asked to send copies of all audit materials, including source documentation. The audit notification will be sent to the Washington University Research Patient Coordinator, who will obtain the audit materials from the participating institution.

Notification of an upcoming audit will be sent to the research team one month ahead of the audit. Once accrual numbers are confirmed, and approximately 30 days prior to the audit, a list of the cases selected for review (up to 10 for each site) will be sent to the research team. However, if during the audit the need arises to review cases not initially selected, the research team will be asked to provide the additional charts within two working days.

Items to be evaluated include:

- Subject screening and enrollment
- Reporting of adverse events
- Maintenance of HIPAA compliance
- Completeness of regulatory documentation
- Completeness of participant documentation
- Acquisition of informed consent
- IRB documentation
- Issues of protocol adherence

Additional details regarding the auditing policies and procedures can be found at <https://siteman.wustl.edu/research/clinical-research-resources/protocol-office-prmcqasmc/>.

## **18 STATISTICAL CONSIDERATIONS**

### **18.1 Study Objectives and Endpoints**

The primary objective is to determine the cCR response rate of patients with stage I-IIIB (cT1-3, N0-2a, M0) rectal cancer being treated with sequential short course radiotherapy followed by multi-drug chemotherapy (either 8 cycles of FOLFOX or 5 cycles of CAPOX). The endpoint is cCR at the completion of short course radiation therapy and chemotherapy. Secondary endpoints include PFS at 2 years, incidence of any grade  $\geq 3$  toxicity during treatment, incidence of post chemoradiotherapy grade  $\geq 3$  toxicity, quality of anorectal function as measured by the FACT-C questionnaire at 1 year, and 1 and 2 year organ preservation rate. Exploratory objectives are to associate tumor microenvironment (including FAK expression) and ctDNA levels with cCR and other clinical outcomes.

### **18.2 Study Design and Sample Size Justification**

The purpose of this phase II study is to determine if the cCR of short course radiation therapy followed by multiple agent chemotherapy in rectal adenocarcinoma is at least 50% in a multi-institution setting. Given that less than one-third of patients with cCR is deemed as an ineffective therapy clinically, our null hypothesis is that cCR rate is 30%. Our phase 1 data indicated a 74% cCR rate but our retrospective study showed 50%, which is more representative of advanced stage and all patients. Therefore, a cCR rate of 50% was considered in the alternative hypothesis. A Simon two-stage design with a 90% power at one-sided 5% type I error will be used to test the null hypothesis. At the first stage, we will enroll 24 patients. If the study continues, 39 additional patients will be needed. Study is not powered for secondary endpoints.

### 18.3 Interim Analyses and Stopping Rules

An interim analysis will be performed on the primary endpoint once 24 subjects have been enrolled and have completed the evaluation after chemotherapy. If  $\leq 8$  patients have cCR in these 24 patients, the study will be stopped for futility. Otherwise, the additional 39 patients will be enrolled. The null hypothesis will be rejected if  $\geq 25$  patients with cCR are observed in 63 patients.

### 18.4 Definition of Evaluability

Endpoint	In order to be evaluable for this endpoint, a patient must...
Primary	
cCR at completion of short course radiation therapy and chemotherapy	Have completed the evaluation after completion of radiation therapy and chemotherapy.
Secondary	
Progression-free survival at 2 years	
Incidence of any grade $\geq 3$ toxicity during treatment	Have received at least one fraction of radiation therapy and one dose of chemotherapy.
Incidence of post chemoradiotherapy grade $\geq 3$ toxicity	
Anorectal function per FACT-C at 1 year	Have completed a FACT-C at baseline and at least one post-treatment time point.
1 and 2 year organ preservation rate	Have received at least one fraction of radiation therapy and one dose of chemotherapy.
Exploratory	
Associate tumor microenvironment with cCR and other clinical outcomes	Have tissue collected at baseline, received at least one fraction of radiation therapy and one dose of chemotherapy, and completed evaluation of their disease.
Associate ctDNA levels with cCR and other clinical outcomes	Have blood collected at baseline and at least one post-dose time point, received at least one fraction of radiation therapy and one dose of chemotherapy, and completed evaluation of their disease.

All eligible enrolled patients that receive any treatment will be included in the intention to treat analysis. Patients that complete protocol therapy (both radiation therapy and chemotherapy) as prescribed will be included in a per protocol analysis.

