### 18.5 Data Analysis

Demographic and clinical characteristics of the sample will be summarized using descriptive statistics. Primary endpoint of the cCR rate will be reported as a proportion with 95% confidence interval (CI), and a one-sided asymptotic Wald test will be performed

to compare the study cohort cCR rate to the null value of 30%. PFS is defined as the time from date of treatment to death or progression, which occurs first. The alive patients without progression are censored as the last date follow-up. Kaplan-Meier method will be used to calculate PFS at 2-year. Proportions of any grade  $\geq 3$  toxicity during treatment, of post chemoradiotherapy grade  $\geq 3$  toxicity and organ preservation rates at 1 and 2 year will be calculated. Their corresponding 95% CIs will also be provided. The quality of anorectal function as measured by the FACT-C questionnaire is collected at screening, completion of chemo, and 1 year after RT. The generalized estimating equation (GEE) model with appropriate link function will be used to analyze this longitudinal data, in which the correlation among the repeated measures from the same patient need be considered. The autoregressive of first order as working correlation structure will be used and the patients with missing values at any time points will be excluded from GEE analysis. Least square means for quality of anorectal function at 1 year after RT will be estimated and 95% CI calculated within the use of GEE sandwich method when accounting for within-patient correlation.

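### Treated patients who miss the post-treatment assessment leave the cCR denominator, and the intention-to-treat set has no stated role for the primary endpoint

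*Combined protocol and SAP*

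**What the plan says.** Section 18.4 gives each endpoint its own evaluability condition. For cCR it is "Have completed the evaluation after completion of radiation therapy and chemotherapy". Below the table come two further sets: "All eligible enrolled patients that receive any treatment will be included in the intention to treat analysis" and "Patients that complete protocol therapy (both radiation therapy and chemotherapy) as prescribed will be included in a per protocol analysis". Neither is tied to an endpoint or ranked against the evaluable set.

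Section 18.3 holds the interim "once 24 subjects have been enrolled and have completed the evaluation after chemotherapy" and stops for futility at 8 or fewer cCR in those 24; Appendix F repeats this. The final rule asks for at least 25 "patients with cCR are observed in 63 patients" and does not say which 63. Section 18.5 uses a one-sided Wald test "to compare the study cohort cCR rate to the null value of 30" percent and reports the rate with a 95% CI. It does not define the cohort. Section 18.7 sets accrual at 63.

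Section 15 describes a response short of cCR through residual disease seen on DRE, endoscopy or MR. It does not mention a patient who was never examined. Appendix F has an NE row in its response table and a column recording whether a patient was replaced, but no text says how NE is scored or when replacement is allowed.

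**The concern.** The assessment comes late. Adding up sections 6.1, 7.1 and 5.3 gives about 1 week of radiotherapy, 2 weeks' gap, 15 weeks of chemotherapy and 3 weeks' wait (21 weeks) at the shortest. At the longest it is 2 + 4 + 16 + 8 weeks plus 4 weeks of permitted delay (34 weeks). Patients who die, withdraw or stop treatment in that time have no documented cCR, and their loss may well be related to poor response. Under the 18.4 condition they count neither as responders nor as failures.

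This is a single-arm trial meant to validate a cCR rate, so the reported proportion is its main result. If unassessed patients are non-responders, leaving them out raises that proportion and its CI, lowers the Wald p-value and makes the futility look easier to pass. Because 18.4 also promises an intention-to-treat analysis without saying what it is for, the headline set could be settled after the data are seen.

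**Working it through.** **Inputs.** From 18.2 and 18.3: null 0.30, alternative 0.50, n1 = 24, stop if 8 or fewer cCR, total 63, reject if 25 or more. The unassessed fraction q is not in the documents; q = 5%, 10% and 15% are assumed, with no responder among the unassessed unless stated.

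**Step 1: the plan's design.** P(reject | p) is the sum over x1 = 9 to 24 of P(Bin(24, p) = x1) × P(Bin(39, p) ≥ 25 − x1).
- p = 0.30: 0.0497. p = 0.50: 0.9033.
- Chance of passing the interim at 0.30: P(Bin(24, 0.30) ≥ 9) = 0.2750.

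The stated 5% and 90% reproduce, so the sample size is not in error.

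**Step 2: what the evaluable set shows.** If the all-treated rate is p, the rate among assessed patients is p/(1 − q). For example, 0.50/0.90 = 0.556 and 0.30/0.90 = 0.333.

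**Step 3: interim.** P(Bin(24, 0.30/(1 − q)) ≥ 9).

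**Step 4: final count rule.** Use the Step 1 formula with rate 0.30/(1 − q), keeping the 25 threshold. Without replacement, 63(1 − q) rounds to 60, 57 and 54 assessed. With replacement, there are 63 assessed.

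| | none lost | 5% | 10% | 15% |
|---|---|---|---|---|
| Reported rate when all-treated rate is 50% | 50% | 52.6% | 55.6% | 58.8% |
| Reported rate when all-treated rate is 30% | 30% | 31.6% | 33.3% | 35.3% |
| Pass interim at all-treated 30% | 27.5% | 33.5% | 40.6% | 48.6% |
| Type I error, 63 enrolled, 25 or more | 4.97% | 5.4% | 5.7% | 5.9% |
| Type I error if replaced to 63 evaluable | 4.97% | 8.4% | 13.8% | 21.9% |

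Without replacement, an unassessed patient adds no cCR to the count under either set, so the final rule moves only because the interim is more lenient. The ceiling, with no interim at all, is P(Bin(63, 0.30) ≥ 25) = 6.4%.

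**Step 5: Wald test and CI.** z = (p̂ − 0.30)/√(p̂(1 − p̂)/n), with 24 cCR among 63 treated.
- 24/63 = 38.1% (95% CI 26.1 to 50.1): z = 1.323, one-sided p = 0.093.
- 24/59 (4 excluded): z = 1.670, p = 0.0475.
- 24/57 = 42.1% (95% CI 29.3 to 54.9; 6 excluded): z = 1.851, p = 0.032.

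**Step 6: the two criteria with nobody lost.** 25/63 rejects under 18.3, but its Wald z is 1.571, p = 0.058. The Wald test at 5% needs 26. Requiring 26 in the two-stage formula gives type I error 3.1% and power 88.5%.

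**Step 7: loss unrelated to response.** The rate among assessed patients is then unchanged. With 60, 57 and 54 assessed and 25 still required, type I error is 3.0%, 1.7% and 0.8%, and power at 50% is 87.6%, 82.4% and 73.4%.

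**Step 8: unassessed scored as not cCR, 63 treated.** If 50% describes all treated patients, Step 1 applies: 4.97% and 90.3%. If 50% describes only assessed patients, the treated rate is 0.50(1 − q) and power is 83.8%, 74.3% and 62.0%.

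**The case against.** The plan is not silent about the set. The cCR row of 18.4 states a rule and 18.3 uses it at the interim, so the natural reading is that the evaluable set governs cCR and the other two sets are supplementary. That stands: a reader might infer that no set is indicated at all, and the documents do not support this. But the indicated set is the one that drops treated patients, and it leaves the promised intention-to-treat analysis without a stated role for cCR.

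The Step 5 example may suggest that the choice of set can reverse the trial's verdict. Under 18.3 it cannot: 24 cCR is below 25 on every set. The reversal appears only if the Wald p-value decides, and no passage gives it priority. It also partly reflects the separate conflict in Step 6.

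Section 15 could be stretched to score an unassessed patient as not cCR, since such a patient does not meet the cCR criteria. Its sub-item, however, calls for residual disease that was observed, and Appendix F lists NE apart from the response categories. Section 15 and Appendix F do provide for documented progression, so a patient with recorded progression need not be unassessed. This may keep the loss small.

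Finally, the direction of bias rests on the assumption that unassessed patients are non-responders. If loss is unrelated to response, the evaluable rate is not inflated and the count rule loses power instead.

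**Conclusion.** The concern holds for the reported cCR rate, its CI, the Wald p-value and the interim look. Under the assumed 5% to 15% loss with no responders among the lost, a true all-treated 50% is overstated by 2.6 to 8.8 percentage points. At a true 30%, the chance of passing futility rises by 6.0 to 21.1 points. The final count rule with 63 enrolled is largely protected, rising by less than one point to 5.9% at most over this range.

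A type I error of 8.4% to 21.9% might be inferred for the trial as planned. It applies only if unassessed patients are replaced to reach 63 evaluable; the Appendix F column hints at replacement, but no text provides for it. The point should be fixed, but it does not invalidate the design.

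**What to change.** In 18.3 to 18.5 and Appendix F:

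- Make the set that 18.4 calls intention to treat (eligible, enrolled, any treatment received) primary for cCR.
- Count any patient without a documented cCR at the post-chemotherapy assessment, including NE, as not cCR.
- State that treated patients are not replaced, and align the Appendix F column with this.
- Apply 8/24, 25/63 and the reported rate and CI to that set. Hold the interim once each of the first 24 treated patients has been assessed or is known to be unassessable.
- Report evaluable and per-protocol rates as sensitivity analyses.
- State that the 18.3 count rule decides and that the Wald test is descriptive. Otherwise 25/63 would still pass one criterion and fail the other.
- State which patients the 50% alternative describes. Section 18.2 supports all treated patients, saying "our retrospective study showed 50%, which is more representative of advanced stage and all patients".

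The cost is wording and, if some patients are unassessed, a slightly lower reported rate. No patients are added if 50% means all treated patients: the count rule keeps 4.97% type I error and 90.3% power. If 50% was meant for assessed patients, power should be restated as 83.8%, 74.3% or 62.0% at 5%, 10% or 15% unassessed, or the sample size revisited.

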## 2 OBJECTIVES

Objectives	Endpoints	Justification for Endpoints
Primary		
To determine the clinical complete response (cCR) rate of patients with stage I-IIIB (cT1-3, N0-2a, M0) rectal cancer being treated with sequential short course radiotherapy followed by multi-drug chemotherapy.	cCR at completion of short course radiation therapy and chemotherapy	Nonoperative management treatment paradigms must be effective at eliciting a clinical complete response.
Secondary		
1. To determine the 2 year progression free survival (PFS) 2. To determine the incidence of any grade $\geq 3$ toxicity during treatment. 3. To determine the incidence of post chemoradiotherapy grade $\geq 3$ toxicity at 1 year 4. To determine quality of anorectal function at 1 year	1. PFS at 2 years 2. Incidence of any grade $\geq 3$ toxicity during treatment 3. Incidence of post chemoradiotherapy grade $\geq 3$ toxicity 4. Quality of anorectal function as measured by the FACT-C questionnaire at 1 year	1. Important to assess disease recurrence, metastasis and death when implementing new treatment paradigm. 2. Important to assess acute toxicity as there is concern that short course radiation is associated with significantly more acute toxicity.

using the FACT-C questionnaire.
 
5. To determine the 1 and 2 year organ preservation rate
	
5. Organ preservation rate at 1 and 2 years
	
3. Important to assess toxicity with new treatment paradigm, especially if rectum is not resected for nonoperative patients.
 
4. Treatment cannot be so toxic that even with preserved rectum patient QOL is poor.
 
5. Patients with cCR may still have regrowth of primary resulting in surgery. Need to assess how many patients can keep their rectum.

Tertiary/Exploratory		

1. To associate tumor microenvironment (including FAK expression) with cCR and other clinical outcomes.
 
2. To associate ctDNA levels with cCR and other clinical outcomes.
		

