## 5.3 Completion of Chemotherapy/Post-Treatment Evaluation

Three to eight weeks after completion of chemotherapy, patients will have the following assessments:

- CEA
- FACT-C questionnaire.
- Surgical assessment w/ endoscopy (sigmoidoscopy preferred, rigid proctoscopy acceptable) to evaluate the extent of residual tumor
- Rectal protocol MRI pelvis to evaluate ycT and ycN stage
- Digital rectal exam (DRE) to evaluate ycT stage

For patients with a cCR, non-operative management will be pursued. For patients with residual disease who do not meet criteria for cCR by 3-8 weeks after completion of the last cycle of FOLFOX or CAPOX, further therapy is recommended and at the discretion of the treating physicians. At investigator discretion, patients who achieve a near clinical complete response with equivocal findings concerning for residual disease may be followed closely with short interval observation (i.e. 6-8 week MR/endoscopic follow-up),

with non-operative management pursued if a subsequent cCR is achieved. Patients whose disease is amenable to transanal endoscopic microexcision (TEM) or local excision (LE) may undergo TEM/LE to evaluate degree of residual disease. For those with ypT1 disease without LVSI present, non-operative management may continue with evaluation noted above. For those with residual ypT2-3 disease or ypT1 with LVSI, extirpative surgery including TME is recommended with treatment at investigators discretion proceeding off-study.

Post-treatment lymph nodes are to be evaluated by imaging and reviewed in multidisciplinary tumor board with a radiologist and classified as progressive, persistent disease, indeterminate or benign. Patients with progressive or persistent lymph node disease will not be eligible for non-operative management and will undergo additional therapy. Patients with indeterminate or benign lymph nodes AND cCR of primary will undergo non-operative management.

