## **11.2 Blood for ctDNA**

Approximately 20 mL of blood will be collected into STRECK tubes (26 mL for first draw) at the following time points:

- Prior to the start of treatment (purple top and 2 STRECK tubes)
- Post-RT labs (with SOC CBC/CMP prior to start of Cycle 1 of chemotherapy)
- Day 1 of Cycle 3 (FOLFOX) or Day 1 of Cycle 2 (CAPOX) (with SOC CBC/CMP)
- Completion of chemotherapy (3-8 weeks after the end of chemotherapy)
- 10-14 months after RT (if this visit aligns with a follow-up time point described below, one draw can be used to satisfy both time points)
- Follow-up months (months 3, 6, 9, 12, 16, 20, 24) until salvage surgery or 2 years from the completion of chemotherapy, whichever is first

Blood will be collected at the hospital lab collection via Natera specimen acquisition form and will be shipped to Natera for processing by the blood collection lab.

Natera, Inc  
[name]  
[name]  
[contact]

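### Section 18.4 sets two conflicting denominators for on-treatment grade ≥3 toxicity and organ preservation, and one of them drops patients who have radiotherapy but never start chemotherapy

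*Combined protocol and SAP*

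**What the plan says.** **Denominator.** In the Section 18.4 table, the rows for on-treatment grade ≥3 toxicity and for organ preservation carry the same condition: "Have received at least one fraction of radiation therapy and one dose of chemotherapy". Below the table, 18.4 adds two analysis sets: "All eligible enrolled patients that receive any treatment will be included in the intention to treat analysis" and "Patients that complete protocol therapy (both radiation therapy and chemotherapy) as prescribed will be included in a per protocol analysis". Neither sentence names an endpoint or says how it relates to the table.

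**Timing and purpose.** Under Section 7.1, chemotherapy starts 2 to 4 weeks after RT ends. Section 2 justifies the toxicity endpoint as follows: "Important to assess acute toxicity as there is concern that short course radiation is associated with significantly more acute toxicity". For organ preservation it says: "Need to assess how many patients can keep their rectum".

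**Analysis.** Section 18.5 reports the toxicity and organ-preservation results as proportions with 95% confidence intervals. In the same paragraph PFS has an event and an origin ("PFS is defined as the time from date of treatment to death or progression, which occurs first"), censoring at last follow-up, and a Kaplan-Meier estimate. Organ preservation is given none of these. Section 18.6 also uses organ preservation as an outcome in logistic regression.

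**The concern.** RT is the first protocol treatment, and there is a planned gap before chemotherapy. A patient can leave the treatment path in that gap because of severe RT toxicity, early death, early surgery or refusal. Under the table, that patient counts in neither rate. For toxicity, the rule can remove the kind of event that Section 2 says the endpoint is there to detect. For organ preservation, it can remove an early resection, which is a failure, or a patient who declined chemotherapy and kept the rectum, which is a success.

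The any-treatment sentence points the other way. An analyst could follow either rule and cite 18.4 for it, so the denominator could be settled after the data are seen.

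The second issue is narrower. A plain proportion at 1 or 2 years needs a known status for every patient at that time. Where follow-up is incomplete, someone must decide whether lost patients are dropped, counted as preserved or counted as failures, and 18.5 does not say which.

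**Working it through.** **What the plan states.** The documents give no figure for either endpoint, so there is none to reproduce. The design's own figures belong to the primary endpoint: stop at ≤8 of 24, reject at ≥25 of 63. Exact binomial calculation gives one-sided alpha 0.0497 and power 0.9033, as planned. These depend only on cCR counts and do not change here.

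**Step 1: choice of set.** Total treated is taken as 63 (Section 18.7). The number of RT-only patients, *k*, and the event rates are assumptions. If *p* is the rate among patients who meet the table rule and *q* the rate among RT-only patients, moving to all treated patients changes the rate by (*k*/63) × (*q* − *p*). The extremes are *q* = 0 and *q* = 1.

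| Endpoint, *k* | Table rule | All treated, *q* = 0 | All treated, *q* = 1 | Shift (points) |
|---|---|---|---|---|
| Toxicity, 1 | 19/62 = 30.6% | 19/63 = 30.2% | 20/63 = 31.7% | −0.5 to +1.1 |
| Toxicity, 3 | 18/60 = 30.0% | 18/63 = 28.6% | 21/63 = 33.3% | −1.4 to +3.3 |
| Toxicity, 5 | 17/58 = 29.3% | 17/63 = 27.0% | 22/63 = 34.9% | −2.3 to +5.6 |
| Organ preservation, 3 | 30/60 = 50.0% | 30/63 = 47.6% | 33/63 = 52.4% | −2.4 to +2.4 |

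The sign depends on whether *q* is above or below *p*, which the documents do not tell us. For scale, the exact 95% interval is 18.8% to 43.2% for 18/60 and 36.8% to 63.2% for 30/60.

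**Step 2: loss to follow-up.** Assume resection at month 7 in 50% of patients, and regrowth surgery in 25% of the rest by month 24 at a constant hazard *h* = −ln(0.75)/17 = 0.01692 per month. The true 2-year rate is 0.5 × 0.75 = 37.5%. Let a fraction *L* of non-operated patients have a loss time spread evenly over months 7 to 24.

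- Lost before resection: *a* = 0.5 × *L* × 0.25/(17*h*) = 0.4345 × *L*.
- Observed with rectum in place at month 24: *b* = 0.375 × (1 − *L*).

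| *L* | *a* | *b* | Lost dropped, *b*/(1 − *a*) | Lost counted as preserved, *a* + *b* | Lost counted as failures, *b* |
|---|---|---|---|---|---|
| 5% | 0.0217 | 0.3563 | 36.4% | 37.8% | 35.6% |
| 15% | 0.0652 | 0.3188 | 34.1% | 38.4% | 31.9% |

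The largest departures from 37.5% are 1.9 and 5.6 points. In this model loss is unrelated to regrowth, so a Kaplan-Meier estimate would target 37.5% in both rows.

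**Step 3: death with the rectum in place.** In the same model without loss, let 5% die by month 24 at a constant hazard. If death is a failure, the rate is 0.375 × 0.95 = 35.6%. If only resection is a failure, the cumulative incidence of resection is 0.4926 + 0.1210 = 0.6136 and the rate is 38.6%. These are two different quantities 3.0 points apart, so the plan must say which one it reports.

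**The case against.** **RT-only patients are already included.** The any-treatment sentence does cover them, and a reader who saw only the table might wrongly infer that the plan removes them outright. The documents do not support that stronger reading. They support a conflict: an endpoint-specific rule that excludes these patients and a general sentence that includes them, with nothing to rank the two.

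**No safety data are lost.** This stands. Section 10 tracks adverse events from the start of treatment, and the monitoring reports in Section 16 summarise toxicity at all sites. Only the reported rate is at issue.

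**Organ preservation is not undefined.** A reader might infer that the event is wholly open. Section 2 speaks of keeping the rectum. Section 5.3 treats local excision as compatible with continued surveillance in one group ("For those with ypT1 disease without LVSI present, non-operative management may continue with evaluation noted above") and names extirpative surgery as a separate step. Read together, these point to rectal resection as the event. The origin is less settled: PFS runs from the date of treatment, while the ctDNA draws in 11.2 run "until salvage surgery or 2 years from the completion of chemotherapy, whichever is first". These are details to write down.

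**A proportion is adequate with complete follow-up.** With the same event definition and no loss, it coincides with Kaplan-Meier, and visits every 3 to 4 months make heavy loss unlikely. At 5% loss the effect is under 2 points; the 5.6-point figure needs 15% loss with every lost patient counted as a failure. This limits the second issue but does not remove it, because 18.5 has no rule even for a few lost patients.

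**The shifts are small.** They lie inside intervals about 24 to 26 points wide. That is fair, but the interval shows sampling error only and does not tell the reader which denominator was used.

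**Conclusion.** The point holds as an unresolved conflict in 18.4 between two denominators for two secondary endpoints. The table's version can exclude patients whose RT-phase course prevented chemotherapy, which fits poorly with the stated reason for the toxicity endpoint. The use of a plain proportion for organ preservation without a rule for incomplete follow-up is a lesser, related gap.

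The size is modest and rests wholly on assumed counts. Three RT-only patients of 63 move toxicity by −1.4 to +3.3 points and organ preservation by ±2.4; five move toxicity by −2.3 to +5.6. Loss of 5% or 15% moves 2-year organ preservation by up to 1.9 or 5.6 points. It would go too far to say that the plan understates toxicity or inflates organ preservation, because either sign is possible. Nor should the cells for PFS and post-chemoradiotherapy toxicity, blank in the table as read, be called omissions; they may be merged cells.

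Section 18.2 says the study is not powered for secondary endpoints. Sample size, the primary cCR test and the futility rule are untouched. This is worth correcting before analysis but does not threaten the trial's main conclusion.

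**What to change.** **(a) Section 18.4.** Make all eligible patients with at least one RT fraction the main set for both rates. Because RT comes first, this is the any-treatment set already described. Keep the RT-plus-chemotherapy set as a sensitivity analysis. Check whether the chemotherapy condition also covers the PFS and post-chemoradiotherapy toxicity rows; if so, align them or say why they differ.

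**(b) Section 18.5.** Estimate 1- and 2-year organ preservation by a time-to-event method from the date of treatment, as for PFS. Use rectal resection as the event and censor patients without resection at last follow-up, with 95% confidence intervals. State how local excision alone is counted. Name in advance one treatment of death with the rectum in place: either a competing event, or a composite of resection or death labelled as such.

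**(c) Section 18.6.** State the binary organ-preservation status used in the logistic regression, including what happens to patients lost before the time point. Censoring does not supply this.

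**Cost.** A few sentences and slight extra analysis work, with no change to sample size, treatment or visits. A resection date is needed. Section 5.4 keeps operated patients in data collection, but Section 14 lists no surgery form and limits the Follow-Up Form to unoperated patients, so one field may have to be added. The reported rates may turn out slightly less favourable.
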